7. Have agreed to undergo serial blood and bone marrow sampling.
8. Be able to understand and willing to sign an informed consent form.
9. Be willing to complete QoL assessments during study treatment and at the designated time points following treatment discontinuation.
10. If female with reproductive potential, must have a negative serum pregnancy test prior to the start of study therapy. Female subjects with reproductive potential are defined as sexually mature women who have not undergone a hysterectomy, bilateral oophorectomy, or tubal occlusion or who have not been naturally postmenopausal for at least 24 consecutive months.

Females of reproductive potential, as well as fertile men with female partners of reproductive potential, must use 2 effective forms of contraception (including at least 1 barrier form) from the time of giving informed consent throughout the study and for 90 days (both females and males) following the last dose of study drug(s). Effective forms of contraception are defined as hormonal oral contraceptives, injectables, patches, intrauterine devices, intrauterine hormone-releasing systems, bilateral tubal ligation, condoms with spermicide, or male partner sterilization. Coadministration of AG-120 may decrease the concentrations of hormonal contraceptives.

Exclusion Criteria:

Subjects who meet any of the following criteria will be excluded from the study:

1. Are candidates for intensive IC for their AML.
2. Have received any prior treatment for AML with the exception of nononcologic treatments to stabilize disease such as hydroxyurea or leukapheresis.
3. Have received a hypomethylating agent for myelodysplastic syndrome (MDS).
4. Subjects who had previously received treatment for an antecedent hematologic disorder, including investigational agents, may not be randomized until a washout period of at least 5 half-lives of the investigational agent has elapsed since the last dose of that agent.
5. Have received prior treatment with an IDH1 inhibitor.
6. Have a known hypersensitivity to any of the components of AG-120, matched placebo, or azacitidine.
7. Are female and pregnant or breastfeeding.
8. Are taking known strong cytochrome P450 (CYP) 3A4 inducers or sensitive CYP3A4 substrate medications with a narrow therapeutic window, unless they can be transferred to other medications within ≥ 5 half-lives prior to dosing.
9. Exclusion Criterion #9 was removed in Protocol Amendment 5, Version 6.0.

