5.3. Azacitidine

The 2017 National Comprehensive Cancer Network (NCCN) Guidelines (V1.2017) recommend use of azacitidine (Vidaza[®]) in patients who are deemed unfit for IC or for intermediate-intensity therapy and for older patients with previously untreated AML (NCCN, 2017). Azacitidine is an analog of the naturally occurring pyrimidine nucleoside cytidine and is classified as an antimetabolite. Azacitidine is approved by the US Food and Drug Administration for 5 subtypes of myelodysplastic syndrome (MDS). Azacitidine is also approved by the European Commission

for the treatment of adult patients who are not eligible for hematopoietic stem cell transplantation with: intermediate and high-risk MDS, according to the International Prognostic Scoring System (IPSS); chronic myelomonocytic leukemia with 10% to 29% marrow blasts without myeloproliferative disorder; and AML with 20% to 30% blasts and multi-lineage dysplasia, according to World Health Organization (WHO) classification.

Azacitidine has been extensively studied in MDS and has been shown in a large, randomized Phase 3 trial of higher-risk MDS subjects to provide a survival advantage of 9.4 months over conventional care regimens, thus altering the natural course of MDS. The median OS of azacitidine-treated subjects was 24.5 months compared with 15.0 months for the combined conventional care regimen group, which included BSC, LDAC, and intensive IC (Fenaux and Ades, 2009). In the subset of 113 subjects in this study who had AML by WHO criteria ($\geq 20\%$ blasts) from the larger MDS group (mean age 70 years, 24% with unfavorable karyotype, median bone marrow blasts 23%), the median OS was 24.5 months (N=55) in the azacitidine arm compared with 16.0 months (N=58) in the conventional care regimen arm (Fenaux and Ades, 2009).

Azacitidine was initially used as a low-intensity treatment for older adults with AML following reports of clinical activity in several small studies. Silverman et al, using WHO AML criteria for diagnosis, reported a median OS of 19.3 months (N=27) in azacitidine-treated subjects compared with 12.9 months (N=25) in subjects who received best standard of care (Silverman et al, 2006). Additionally, Goldberg et al, reported on 33 subjects who received azacitidine (N=11, median age 74 years) or 7+3 intensive IC (N=22, median age 67 years). The median OS was 13.2 months in azacitidine-treated subjects compared with 9.2 months in intensive IC-treated subjects (Goldberg et al, 2006).

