12.2. Analysis Sets

The following analysis sets will be evaluated and used for presentation of the data:

- Intent-to-Treat (ITT) Analysis Set: All subjects who are randomized. Subjects will be classified according to the randomized treatment arm. The ITT Analysis Set will be the default analysis set for all analyses, unless otherwise specified.
- Safety Analysis Set (SAS): All subjects who received at least 1 dose of the study treatment. Subjects will be classified according to the treatment received. The SAS will be the primary analysis set for all safety analyses, unless otherwise specified.
- Per-Protocol Analysis Set (PPAS): All subjects in the ITT who have no major protocol deviations. Additional efficacy analyses may be performed using the PPAS. Rules for major protocol deviations resulting in exclusion from the PPAS will be specified in the SAP.
- Pharmacokinetic Analysis Set (PAS): All subjects who have at least 1 post-dose blood sample providing evaluable PK data for AG-120.

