5. ANALYSIS DATA SETS

Only subjects who sign informed consent and are screened will be included in the analysis sets below.

The following analysis sets will be evaluated and used for presentation of the data:

- The Full Analysis Set (FAS) will include all subjects who are randomized. Subjects will be classified according to the randomized treatment arm. (Note: this data set is referred to as the Intent-to-Treat Analysis Set in the protocol.)
- The Safety Analysis Set will include all subjects who receive at least 1 dose of the study treatment. Subjects will be classified according to the treatment received, where treatment received is defined as:
 - The randomized treatment if it is received at least once, or
 - The first treatment received if the randomized treatment is never received
- The Per-Protocol Set (PPS) is a subset of the FAS. Subjects who meet any of the following criteria will be excluded from the PPS:
 - Do not receive at least 1 dose of the randomized treatment
 - Eligible for intensive chemotherapy (IC) (ie, do not meet Inclusion Criterion 1)
 - Do not have an IDH1 mutation as determined by central laboratory testing (ie, do not meet Inclusion Criterion 3)
 - Have an ECOG PS score >2 (ie, do not meet Inclusion Criterion 4)
 - Have received any prior treatment for AML with the exception of noncolytic treatments to stabilize disease such as hydroxyurea or leukapheresis (ie, do not meet Exclusion Criterion 2)
 - Have received any prior hypomethylating agent (ie, do not meet Exclusion Criterion 3)
 - Have received any prior IDH1 inhibitor (ie, do not meet Exclusion Criterion 5)
- The Biomarker Analysis Set (BAS) is a subset of the FAS and will include all subjects who have at least 1 on-treatment biomarker sample providing valid IDH1m variant allele frequency (VAF) data.

Table 2 summarizes the use of the analysis sets.

Table 2: Analysis Sets for Each Endpoint

Endpoints	Full Analysis Set (FAS)	Per-Protocol Set (PPS)	Safety Analysis Set	Biomarker Analysis Set (BAS)
Demographic and other baseline characteristics	✓		✓	
Disposition	✓			
Major protocol deviations	✓			
Subsequent therapies	✓			
Exposure and concomitant therapies			✓	
Efficacy	✓	✓ (primary and key secondary only*)		
Safety			✓	
Biomarkers				✓

* Key secondary endpoints are CR, OS, CR+CRh and objective response (OR).

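### The SAP's Per-Protocol Set drops anyone with any prior hypomethylating agent and calls this Exclusion Criterion 3, which bars such an agent only when given for MDS

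*Protocol*

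**What the plan says.** Exclusion Criterion 3 has the same wording in the Protocol synopsis and in Section 8.3: "Have received a hypomethylating agent for myelodysplastic syndrome (MDS)". Exclusion Criterion 2 separately bars prior treatment for AML, apart from measures to stabilize disease. Exclusion Criterion 4 deals with "Subjects who had previously received treatment for an antecedent hematologic disorder". It does not bar them outright, but says that they "may not be randomized until a washout period of at least 5 half-lives of the investigational agent has elapsed".

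Protocol 12.2 defines the Per-Protocol Set as "All subjects in the ITT who have no major protocol deviations" and leaves to the SAP the rules for which major deviations lead to exclusion. SAP Section 5 gives those rules as a list. The bullet at issue is "Have received any prior hypomethylating agent (ie, do not meet Exclusion Criterion 3)".

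SAP Table 2 assigns the Per-Protocol Set to the primary and key secondary efficacy endpoints. SAP 7.7 bases the efficacy analyses on the Full Analysis Set unless stated otherwise. SAP 7.7.1.2 uses the Per-Protocol Set for the third EFS sensitivity analysis.

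**The concern.** The bullet claims to restate a protocol criterion but is wider than that criterion. A subject whose earlier hypomethylating agent was given for something other than MDS or AML can satisfy every eligibility criterion and still be removed. The set would then not be the one that Protocol 12.2 describes.

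The subjects at risk have had the same drug class as the azacitidine backbone, so they may differ in prognosis from the rest of the trial. If results differ between the full and per-protocol sets, a reader will attribute the difference to protocol violations, when part of it could come from removing compliant subjects. If the mismatch is noticed only at analysis, someone must decide after the fact whether the descriptive words or the cited criterion governs.

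**Working it through.** **Step 1. Classify prior use by indication.**

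| Agent given for | Protocol | SAP Per-Protocol Set | Agree? |
|---|---|---|---|
| MDS | Barred by Exclusion Criterion 3 | Removed | Yes |
| AML | Barred by Exclusion Criterion 2 | Removed (also under the Criterion 2 bullet) | Yes |
| Another disorder | Not barred by Criterion 2 or 3; Criterion 4 foresees prior treatment of an antecedent hematologic disorder | Removed | No |

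**Step 2. Can the third row contain an eligible subject?** Exclusion Criterion 11 bars a prior malignancy but exempts MDS and myeloproliferative disorder. SAP 7.1 codes a history of myeloproliferative disorder as one form of secondary AML, so this history is expected in the trial. A subject who had a hypomethylating agent for that disorder, and who meets the other criteria, is eligible.

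**Step 3. Which part of the bullet governs?** The parenthesis says that the subject does not meet Exclusion Criterion 3. A violator meets an exclusion criterion, so read literally the parenthesis describes compliant subjects and would remove nearly everyone. The lead words must therefore govern, and those are the wider ones.

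**Step 4. Size (illustration only).** The documents give no count. Assume 0 to 4 subjects, that is 0 to 2% of 200, all removed from the AG-120 arm, and ignore stratification. The inputs are the design values in Protocol 12.12: 100 subjects per arm, CR by 24 weeks of 40% against 20%, and 173 events.

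- Treatment failures, all placed on Day 1: 60 + 80 = 140. Expected in the AG-120 arm: 140 × 100/200 = 70. Observed minus expected: 60 − 70 = −10.00.
- Day 1 variance: 100 × 100 × 140 × 60 / (200² × 199) = 10.55. The other 173 − 140 = 33 events occur among responders split about 40 to 20, so each adds about (2/3)(1/3) = 0.222, or 7.33 in all. The total is about 17.9, with square root 4.23.
- Remove one AG-120 failure: expected 139 × 99/199 = 69.15; difference 59 − 69.15 = −10.15. The change of −0.15 gives about −0.15/4.23 = −0.04 in z.
- Remove four AG-120 failures: expected 136 × 96/196 = 66.61; difference 56 − 66.61 = −10.61. The change in z is about −0.61/4.23 = −0.14.
- Remove one AG-120 responder: expected 140 × 99/199 = 69.65; difference 60 − 69.65 = −9.65. The change in z is about +0.35/4.23 = +0.08.
- Remove four AG-120 responders: expected 140 × 96/196 = 68.57; difference 60 − 68.57 = −8.57. The change in z is about +1.43/4.23 = +0.34.

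Negative values favor AG-120. These figures use the Day 1 term with the variance held fixed; removing a responder also alters later terms. The sign depends on the arm and outcome of the removed subject. All four coming from one arm with one outcome is an extreme case.

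**The case against.** **The SAP is entitled to set these rules.** Protocol 12.2 delegates the rules to the SAP, and SAP Section 2 says that the SAP may modify protocol plans. That stands as far as it goes: the SAP may choose which deviations count, and its list need not cover every criterion. But the delegation concerns major deviations, and an eligible subject has none on this point. The bullet also cites Criterion 3 as its equivalent, which reads as a restatement and not as a deliberate extension.

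**The affected group may be empty.** This stands. The Protocol's section on azacitidine lists "chronic myelomonocytic leukemia with 10% to 29% marrow blasts without myeloproliferative disorder" as a use distinct from MDS, and a reader might take it as the natural example. It is a doubtful one. If that disease is not counted as MDS, Exclusion Criterion 11 would generally bar the subject; if it is counted as MDS, Criterion 3 applies. The myeloproliferative example avoids this problem, but the documents describe no such use of a hypomethylating agent.

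**Prior therapy is fixed before randomization.** This also stands. Excluding on it does not by itself bias the comparison between arms. What changes is the population described, not the validity of the randomized contrast.

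**A reader might infer that the list also fails the other way, by keeping candidates for intensive chemotherapy aged 75 or over.** The SAP bullet is "Eligible for intensive chemotherapy (IC) (ie, do not meet Inclusion Criterion 1)" and does not cite Exclusion Criterion 1, "Are candidates for intensive IC for their AML". The documents do not support that reading. Inclusion Criterion 1 is the protocol's own definition of ineligibility for intensive chemotherapy, and age 75 or over is enough to meet it. Exclusion Criterion 1 has no separate definition that such a subject could be shown to breach. The bullet's lead words would in any case remove a true candidate of any age. To make the argument, one would have to let the parenthesis override the lead words here and do the opposite for hypomethylating agents.

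**Conclusion.** The point holds for the hypomethylating-agent bullet only, and it is minor. The SAP's words are wider than the criterion that they cite, and an eligible subject treated for a disorder other than MDS or AML would be dropped from the Per-Protocol Set without a deviation.

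The effect is confined to the per-protocol analyses of EFS and the key secondary endpoints. The primary result does not move. The number of subjects is not documented and may be zero. If it were one, the per-protocol EFS statistic would shift by roughly 0.04 to 0.08 in z on the assumptions above. Four, all from one arm with the same outcome, would shift it by roughly 0.14 to 0.34.

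The phrase saying that violators do not meet Exclusion Criteria 2, 3 and 5 is inverted, but it is a clerical slip: the lead words leave no doubt who is meant.

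One assumption remains. The SAP is written for protocol Version 7.0 and the protocol supplied is Version 10.0. The amendment history, which covers major changes only, records no later change to these criteria, but the Version 7.0 text cannot be checked.

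**What to change.** In SAP Section 5, change the bullet to: *received a hypomethylating agent for MDS (meets Exclusion Criterion 3)*. If the sponsor does want any prior hypomethylating agent to remove a subject, write that as a separate Per-Protocol Set rule, without equating it with Criterion 3, and reconcile it with Protocol 12.2 and the eligibility criteria. Either choice should be made before unblinding.

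As editorial corrections, say that the subject meets the exclusion criterion in the bullets for Exclusion Criteria 2, 3 and 5.

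The cost is a wording change to three bullets. The indication for any prior hypomethylating agent is already needed to apply Criterion 3 at screening, so no new assessment is required, and neither the sample size nor the primary analysis is affected.

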At the time of the primary endpoint analysis (approximately 173 EFS events or as deemed necessary by the IDMC), the study will be unblinded. Subjects on treatment at that time may continue receiving study drug. After the primary endpoint analysis, and if the benefit-risk profile favors treatment, subjects randomized to placebo may be offered the choice to receive active AG-120. End of Study is defined as the time at which all subjects have died, discontinued the study, are lost to follow-up, or have withdrawn consent; or when the Sponsor ends the study.

Study Assessments: See Schedule of Assessments in body of protocol.

Criteria for Evaluation:

During treatment, response will be evaluated by the Investigator based on modified IWG Response Criteria for AML and European LeukemiaNet guidelines to determine subject status and continuation on study treatment; CRh will be derived by the Sponsor.

Primary Endpoint:

The primary endpoint of the study is EFS, which is defined as the time from randomization until treatment failure, relapse from remission, or death from any cause, whichever occurs first. Treatment failure is defined as failure to achieve CR by Week 24.

Key Secondary Endpoints:

- CR rate (CR defined as bone marrow blasts <5% and no Auer rods, absence of extramedullary disease, ANC $\geq 1.0 \times 10^9/L$ [1000/ μL], platelet count $\geq 100 \times 10^9/L$ [100,000/ μL], and independence of RBC transfusions).
- OS, defined as the time from date of randomization to the date of death due to any cause.
- CR + CRh rate (CRh is defined as a CR with partial recovery of peripheral blood counts where ANC is $>0.5 \times 10^9/L$ [500/ μL], and platelet count is $>50 \times 10^9/L$ [50,000/ μL]; CRh will be derived by the Sponsor).
- ORR, defined as the rate of CR, CRi (including CRp), PR, and MLFS.

Additional Secondary Endpoints:

- CR + CRi (including CRp) rate (CRi [including CRp] is defined as all CR criteria except for residual neutropenia where ANC is $<1.0 \times 10^9/L$ [1000/ μL] or thrombocytopenia where platelet count is $<100 \times 10^9/L$ [100,000/ μL]; without platelet transfusion for at least 1 week prior to disease assessment).
- DOCR, among subjects who achieved CR; DOCRh, among subjects who achieved CR or CRh; DOR, among subjects who achieved CR, CRi (including CRp), PR, and/or MLFS; and DOCRI, among subjects who achieved CR or CRi (including CRp).

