Event-free survival is defined as the time from randomization until treatment failure, relapse from remission, or death from any cause, whichever occurs first. Treatment failure is defined as failure to achieve CR by Week 24. Subjects who do not achieve CR by Week 24 will be considered to have had an event at Day 1 of randomization. For the remaining CR responders, the event time will be the time of either disease relapse or death, whichever occurs first. Event-free survival will be censored upon initiation of a new anticancer therapy should a new therapy be initiated prior to any EFS event. Sensitivity analyses will be performed to explore the robustness of the primary analysis results and will include an analysis based on the stratified log-rank test following the Intent-to-Treat principle, where the time of relapse or death is determined using the actual date of relapse or death without censoring for missing disease assessments or start of subsequent anticancer therapy.

No interim analyses for efficacy are planned. The analysis for the primary endpoint EFS will be performed at the time when 173 EFS events have occurred or as deemed necessary by the IDMC. Event-free survival will be tested using the log-rank test stratified by the randomization stratification factors (de novo status and geographic region). The basis for a claim of efficacy will be the statistical significance of EFS in favor of the AG-120 + azacitidine arm when the 1-sided $p \leq 0.025$ (observed EFS hazard ratio [HR] ≤ 0.742).

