9.11.2. End of Study

At the time of primary endpoint analysis (approximately 173 EFS events or as deemed necessary by the IDMC), the study will be unblinded. Subjects on treatment at that time may continue receiving study drug. After unblinding, and if the benefit-risk profile favors treatment, subjects randomized to placebo may be offered the choice to receive AG-120. End of Study is defined as the time at which all subjects have died, discontinued the study, are lost to follow-up, or have withdrawn consent; or when the Sponsor ends the study.

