12. STATISTICAL METHODS

12.1. General Statistical Methods

Summaries will be produced for subject disposition, demographic and baseline disease characteristics, efficacy, safety, PK, and PD, as appropriate. Categorical data will be summarized by frequency distributions (number and percentages of subjects). Continuous data will be summarized by descriptive statistics (mean, standard deviation, median, minimum, and maximum). Time-to-event endpoints will be estimated using the Kaplan-Meier (KM) method. Point estimates and 95% CIs will be provided where appropriate, and estimates of the median and other quantiles, as well as individual time points (eg, 3-, 6-, and 12-month rates), will be produced.

All data will be provided in by-subject listings.

The study data will be analyzed and reported in the clinical study report (CSR) based on all subjects' data up to the time when 173 EFS events have been reached in the study. Complete details for all analyses will be provided in the statistical analysis plan (SAP).

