12.5.1. Analyses of the Primary Endpoint

The analysis for the primary endpoint will be performed at the time when 173 EFS events have occurred. Event-free survival is defined as the time from randomization until treatment failure, relapse from remission, or death from any cause, whichever occurs first. Treatment failure is defined as failure to achieve CR by Week 24. Subjects who do not achieve CR by Week 24 will be considered to have had an event at Day 1 of randomization. For the remaining CR responders, the event time will be the time of either disease relapse or death, whichever occurs first. Event-free survival will be censored upon initiation of a new anticancer therapy should a new therapy be initiated prior to any EFS event.

Event-free survival will be tested using the log-rank test stratified by the randomization stratification factors (de novo status and geographic region) based on the data in the ITT Analysis Set. The basis for a claim of efficacy will be the statistical significance of EFS in favor of the AG-120 + azacitidine arm when the 1-sided $p \leq 0.025$ (observed EFS HR ≤ 0.742).

The distribution of EFS will be estimated using the KM method. The KM curves and 25th, 50th (median), and 75th percentiles (if estimable), along with their 2-sided 95% CIs, will be presented for each treatment arm. The KM estimates at individual time points (eg, 3-, 6-, and 12-month rates) will also be presented for each treatment arm. A Cox regression model stratified by randomization stratification factors will also be used to estimate the HR of EFS. However, given that the assumption of proportional hazards is not met based on the EFS definition, the overall HR is less meaningful in this context. As EFS is a composite endpoint, the estimates presented separately by each component are more meaningful: CR rate by 24 weeks and EFS among those who have achieved CR by 24 weeks. For subjects who achieve CR by 24 weeks, the KM curves

of the EFS distribution and 25th, 50th (median), and 75th percentiles (if estimable) along with their 2-sided 95% CIs will be presented for each treatment arm. A Cox regression model stratified by randomization stratification factors will also be used to estimate the HR of EFS for these subjects. In addition, the ratio of restricted mean survival time, which does not rely on proportional hazards assumptions, between the 2 arms will also be presented to summarize the treatment effect.

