2. INTRODUCTION

This SAP provides the detailed methodology for summary and statistical analyses of the data collected in Study AG120-C-009, except for pharmacokinetic (PK)/pharmacodynamic (PD) data, which will be described in a separate SAP. This document may modify the plans outlined in the protocol; however, any major modifications of the primary endpoint definition or its analysis will also be reflected in a protocol amendment.

The clinical study report (CSR) will include all data up to a data cutoff date that is determined based on the number of events required for the final analysis of the primary endpoint [event-free survival (EFS)] and a minimum follow-up of 24 weeks for all subjects randomized.

The data cutoff date will be defined prospectively once a data extract [before database lock (DBL)] is available that indicates that all subjects have been randomized and have the minimum duration of follow-up and that the required number of events for EFS is expected to occur by the cutoff date. The final number of events might deviate from the planned number; the data cutoff date will not be adjusted retrospectively in this case.

End of Study (EOS) is defined as the time at which all subjects have died, discontinued the study, are lost to follow-up, or have withdrawn consent; or when the Sponsor ends the study.

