6.2.2. Decision Rules

The final analysis for the primary and key secondary efficacy endpoints will be performed after all subjects have been randomized in the study and followed for a minimum of 24 weeks and the target number of events for EFS has occurred (see [Section 2](#)).

The basis for a claim of efficacy will be the statistical significance of EFS in favor of the AG-120+azacitidine arm when the 1-sided p-value <0.025. To protect the integrity of the study and to preserve the Type 1 error at or below 1-sided $\alpha=0.025$, a hierarchical testing strategy will be used as described in [Section 6.2.1](#) to test each of the key secondary efficacy endpoints and statistical significance will be achieved with 1-sided p-value <0.025 for each endpoint.

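### The Protocol's Synopsis and Section 9.11.2 let the IDMC call the confirmatory EFS analysis, a route that Sections 12.1 and 12.5.1 and the SAP lack and that has no criterion or alpha rule

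*Protocol*

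**What the plan says.** The documents give three different triggers for the confirmatory analysis.

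- **173 events or the IDMC.** In the Protocol Synopsis (Analysis for the Primary Endpoint) the EFS analysis is "performed at the time when 173 EFS events have occurred or as deemed necessary by the IDMC". The Synopsis (End of Study) adds: "At the time of the primary endpoint analysis (approximately 173 EFS events or as deemed necessary by the IDMC), the study will be unblinded". Section 9.11.2 repeats "approximately 173 EFS events or as deemed necessary by the IDMC".
- **173 events only.** Protocol Section 12.5.1: "The analysis for the primary endpoint will be performed at the time when 173 EFS events have occurred". Section 12.1 bases the study report on "data up to the time when 173 EFS events have been reached in the study".
- **Randomization complete, follow-up and events.** SAP Section 2 adds to the event count "and a minimum follow-up of 24 weeks for all subjects randomized", and fixes the cutoff in advance: "The data cutoff date will be defined prospectively once a data extract". SAP Section 6.2.2 has all subjects randomized, "followed for a minimum of 24 weeks and the target number of events for EFS has occurred". There is no IDMC route.

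The Synopsis, Protocol Sections 10.6.1, 12.5 and 12.10, and SAP Section 7.10 all say that no interim efficacy analysis is planned. Section 12.5 claims control of the overall error at 1-sided 2.5% through a fixed sequence that starts with EFS.

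On the IDMC itself, Section 9.5 has it reviewing unblinded data that include efficacy. Section 10.6.1 lists demographic and safety data only, limits its recommendations to continuing, amending or stopping, leaves the decision to the sponsor, and puts the review requirements in a charter.

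**The concern.** A committee that, on one reading, sees unblinded EFS data may prompt the confirmatory EFS test at a time of its choosing. Neither the Protocol nor the SAP says what would make that necessary, how many events it needs, or at what level the test would be made. The only level given is the full 1-sided 0.025.

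If a call followed favourable EFS results, the trial would in effect have had an unplanned efficacy look. The error of the first test in the fixed sequence, which opens the way to CR, OS, CR+CRh and ORR, would then exceed 2.5%. An early call would also bring OS forward. Section 12.13.1 gives OS 54% power at about 145 deaths, and an earlier cutoff would have fewer.

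**Working it through.** **1. The plan's own figures.** Accrual (Section 12.12): 3×10 + 5×34 = 200 over 44 months. Critical HR: exp(−2×1.96/√173) = 0.742, as stated. Simulated power of the stated design at 173 events, with an unstratified log-rank test, is 81.3% against the stated 80%. These figures reproduce. The defect is the undefined second trigger.

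**2. When the SAP's follow-up condition is met.** 24 weeks = 168/30.4375 = 5.52 months, so the last subject reaches 24 weeks at 44 + 5.52 = month 49.5. Subjects with 24 weeks of follow-up:

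- Month 36: 30 + 5×(36 − 5.52 − 10) ≈ 132 of 200.
- Month 42: 30 + 5×(42 − 5.52 − 10) ≈ 162 of 200.

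The Protocol expects the analysis at about month 52. In one simulation the 173rd event fell at a median of month 48.7, which depends on the dropout and timing assumed. Even the 173-events-only wording and the SAP can therefore point to different dates.

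**3. Type I error if favourable EFS prompts the call.** The documents give no timing, so months 36, 42 and 48 are assumptions. The model is one extra look at 1-sided 0.025, claiming success if it is crossed and otherwise continuing to the planned analysis.

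The analytic check uses two normal statistics with correlation √t, where t is the information fraction at the extra look. Total error is 4.2% at t = 0.5, 3.8% at 0.7, 3.5% at 0.8 and 3.2% at 0.9.

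Null simulations of the actual endpoint (failures dated Day 1, exponential EFS in responders, planned accrual, 5% dropout, early looks restricted to subjects with 24 weeks of follow-up):

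| Simulation | Month 36 | Month 42 | Month 48 | No extra look |
|---|---|---|---|---|
| Stratified, 3 null scenarios × 2 assumed stratum mixes, 40,000 trials each | 4.0–4.2% | 3.6–3.9% | 3.0–3.3% | 2.5–2.7% |
| Unstratified, 15,000 trials | 4.2% | 3.9% | 3.2% | 2.7% |
| Unstratified, 8,000 trials | 3.7% | 3.4% | 2.7% | 2.2% |

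The Monte Carlo standard error at 2.5% is √(0.025×0.975/n): 0.08 points for 40,000 trials and 0.17 for 8,000. The third row sits lower throughout, but its increments over no look are similar.

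**4. Other reasons for a call.** A single analysis at one of those months for reasons unrelated to EFS gives 2.4–2.7%. With a look at month 42 (unstratified, no dropout, 12,000 trials), a call prompted by unfavourable EFS gives 2.66%, the same as no look. A call prompted by favourable EFS gives 3.78%.

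**5. Secondary: the HR of 0.742.** The formula in step 1 takes the log-rank variance as d/4 = 173/4 ≈ 43. Most events are tied at Day 1, so under the design assumptions the simulated variance is about 16.5 stratified and 17.9 unstratified, at about 176 events. The HR threshold and the p-value therefore do not coincide. How often HR ≤ 0.742 occurs with p > 0.025 depends on how ties are handled:

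- Efron ties: 3.6% and 5.3% in two runs, with about 0.9% discordant the other way. The mean HR is 0.638–0.639, close to the Protocol's 0.641.
- The discrete method in SAP Section 7.7.1.1: 13.5% stratified and 11.0% unstratified, none the other way.

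**The case against.** The strongest reply is that nobody has proposed an early look. Both documents repeatedly rule one out, Section 12.1 leaves full analysis detail to the SAP, and the SAP trigger is explicit with a prospective cutoff. The IDMC wording may cover only a recommendation to stop, and the charter may govern it. The SAP is written to Protocol Version 7.0 while the Protocol is Version 10.0, so part of the difference between them may be version lag.

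Much of this stands, and it limits the point. It does not remove the conflict inside the current Protocol between the Synopsis and Section 9.11.2 on one side and Sections 12.1 and 12.5.1 on the other. If stopping is what the wording covers, the Protocol should say so and say how EFS would then be analysed.

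Three stronger inferences are tempting and are not supported:

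- **That the wording by itself inflates the error, or that any EFS-dependent call does.** Only a call prompted by favourable EFS does so.
- **That the Protocol and SAP can never both be followed.** They clash on follow-up only for a call before about month 49.5. A later call meets that condition, and one made after 173 events also meets the event target.
- **That 0.742 is a miscalculation, or is discordant with the p-value in 11–14% of trials without qualification.** The arithmetic is right. The 11–14% figure uses the SAP's discrete-ties HR, which no passage pairs with 0.742. The Protocol itself calls the overall HR less meaningful.

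**Conclusion.** The trigger for the confirmatory EFS analysis is contradictory within the Protocol and between the Protocol and the SAP. In those two documents the IDMC route has no criterion, boundary or alpha rule. That rests on the text alone; the unseen charter might supply a rule but would not remove the contradiction.

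The numerical consequence is conditional. With one extra unadjusted look prompted by favourable EFS, type I error would be roughly 3 to 4% instead of 2.5%. The look months, stratum shares and dropout pattern behind that figure are assumptions, so it shows order of magnitude only. Breach of the SAP's minimum follow-up is likewise confined to early calls on planned accrual.

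The mismatch between 0.742 and the p-value is real but secondary: about 4–5% of trials with Efron ties, more with discrete ties.

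**What to change.** 1. Delete the IDMC alternative as a trigger for the confirmatory EFS analysis in the Synopsis (End of Study; Analysis for the Primary Endpoint) and Section 9.11.2. Use the SAP Section 6.2.2 trigger throughout, including Sections 12.1 and 12.5.1.
2. Align the EFS follow-up wording, which carries the same phrase: Synopsis (Methodology; EFS Follow-up), Sections 7.1, 8.5.2, 9.11.1 and 10.1, and Table 6 footnote 4.
3. If the route is kept, either limit it to reasons unrelated to favourable EFS results or prespecify an alpha-spending boundary, with information measured by the log-rank variance.
4. State how EFS is analysed if the study stops on an IDMC recommendation.
5. Reconcile Sections 9.5 and 10.6.1 on which data the IDMC sees.
6. Base the claim on the log-rank p-value alone, as SAP Section 6.2.2 does, and remove 0.742 from the Synopsis and Section 12.5.1.

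All of this is wording except the spending option, whose cost is small. With an O'Brien-Fleming-type Lan-DeMets function and one look at month 42 (information fraction about 0.775), the early level is 2×[1 − Φ(2.2414/√0.775)] = 0.0109 and the final level 0.0218. Simulated overall power is 81.8% against 82.0% with no look, and type I error is 2.5–2.6%.
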